2.4.2 Minimization of Bias

There will be no specific gender or ethnic background for enrollment and the decision to approach for consent will be by convenience of team members.

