2.3 Patient Selection

2.3.1 Inclusion Criteria

Each subject must meet all of the following criteria:

1. Age >18 years
2. Acute kidney injury or acute kidney disease
3. Retroperitoneal ultrasound ordered or performed within the last 4 hours

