2.4.1 Study Procedures

CONFIDENTIAL: This document is the intellectual property of [name]. Acceptance of this document constitutes the agreement by the recipient that no unpublished information contained herein will be published or disclosed without prior written approval.

The study team will identify potential participants based on inpatient orders placed in EPIC for a radiology-performed renal ultrasound. Once an order in EPIC has been placed for a renal ultrasound to be done by radiology on a patient that is admitted to Barnes Jewish Hospital, a team member will discuss the study with participants in person.

All patients that fit inclusion/exclusion criteria will be invited to consent and take part in the study. The recruiting investigator will meet individually with each patient and describe the study to them. Patients will either be in the emergency department, on the floor (South or North campus in BJH) or in the ICU. Investigator will spend the necessary time to explain the study to each patient and answer all questions.

Patients will be told that taking part in the study is purely voluntary and that they can decline to be involved. This will not affect their medical care.

Patients will be told that they can withdraw from the study at any time after enrolling.

Team member will make sure that patients interested in study participation are in a quiet area. Team member will review the consent and answer all study related questions.

Upon consent of patient, patient's age and gender with the assigned study code number will be recorded on enrollment log. Study code number, patient name and MRN will be written on bedside data collection sheet.

One non-invasive hand-carried renal ultrasound will be performed the following way:
MD performs right and left sided renal ultrasound and notes his findings on data collection sheet and places in envelope

Each enrolled patient will have the following ultrasound images recorded within 4 hours of completion of the radiology-performed renal ultrasound:

Right kidney longitudinal view

Right kidney mid transverse view

Left kidney longitudinal view

Left kidney mid transverse view

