2.4.6 Observations and Measurements

1. Presence or absence of hydronephrosis in the right kidney
2. Presence or absence of hydronephrosis in the left kidney
3. If hydronephrosis present: severity of hydronephrosis (mild, moderate, severe)
4. Time taken to obtain ultrasound images of both kidneys
5. Technical difficulty of study as rated by operator (easy, relatively easy, challenging, very challenging)

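### Section 2.4.2 leaves the approach to team members' convenience and no record of eligible patients not enrolled is planned, so discretionary selection is neither prevented nor made visible

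*Combined protocol and SAP*

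**What the plan says.** All references are to the combined protocol and SAP.

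- **Who is approached.** Section 2.4.1 states: "All patients that fit inclusion/exclusion criteria will be invited to consent and take part in the study". Section 3.3 repeats the sentence. Section 2.4.2, after saying that no gender or ethnic group is targeted, adds that "the decision to approach for consent will be by convenience of team members". Nothing else stands under that heading.
- **When.** Section 2.4.1 starts recruitment "Once an order in EPIC has been placed for a renal ultrasound to be done by radiology". The third inclusion criterion in Section 2.3.1 is wider: "Retroperitoneal ultrasound ordered or performed within the last 4 hours". A patient can therefore enter after the reference scan.
- **By whom.** Section 2.4.1 says "The recruiting investigator will meet individually with each patient" and, separately, "MD performs right and left sided renal ultrasound". It does not say whether these are the same person.
- **Blinding.** Section 2.4.6.3 mentions it for obtaining the data. No section extends it to the decision to approach.
- **What is recorded.** Once the patient has consented, "age and gender with the assigned study code number will be recorded on enrollment log". No section plans a count of patients who were eligible, approached or declining, or reasons for non-enrolment.

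**The concern.** The four accuracy measures in Section 2.4.6.3 are the primary outcomes, and all depend on who is enrolled. If easier scans are over-represented, sensitivity and specificity shift. If the share with hydronephrosis changes, PPV and NPV shift. A larger sample would not remove either effect.

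Two routes are left open. A team member might pass over a patient who looks hard to scan; the plan itself expects scans to vary, since it collects "Technical difficulty of study as rated by operator". Or, where recruiter and scanner are different people and the radiology scan is already done, the recruiter might know the reference result when deciding whom to approach. The plan provides for neither, but it excludes neither.

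Without the numbers eligible, approached and enrolled, a reader cannot judge how well the sample represents patients meeting Sections 2.3.1 and 2.3.2.

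**Working it through.** **1. The passages side by side.** Sections 2.4.1 and 3.3 set a rule of inviting all eligible patients. Section 2.4.2 lets staff convenience decide.

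- *Availability reading:* every eligible patient is invited when a team member is free. The passages then largely agree, and the sample depends on time of day and staffing.
- *Discretion reading:* staff may choose among eligible patients. The passages then conflict.

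The text does not settle which is meant. On either reading there is no denominator.

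**2. Indirect evidence.** The EPIC orders (Section 2.4.1), the difficulty ratings of enrolled scans (Section 2.4.6) and the radiology results (Section 3.2.1) could give partial evidence afterwards. No such use is planned.

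**3. The plan's own figure.** Section 2.4.6.6 gives 170 patients, margin 0.07, prevalence 90% (read here as absence of hydronephrosis) and specificity 90%. The usual precision formula gives 1.96² × 0.90 × 0.10 / 0.07² = 70.6 patients without hydronephrosis, and 70.6 / 0.90 = 78.4, so 79 in total. It does not reproduce 170. That is a separate matter; below, 170 is taken simply as the number enrolled.

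**4. Precision at 170.** 170 × 0.90 = 153 without and 17 with hydronephrosis. The half-width is 1.96 × √(0.9 × 0.1 / n), with sensitivity also assumed to be 90%:

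- specificity, n = 153: 4.8 points
- sensitivity, n = 17: 14.3 points

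**5. Illustrative shift.** Shift = (excess share of easy scans) × (accuracy in easy scans minus accuracy in hard scans). Both inputs are assumed; the documents give neither.

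- Excess share 5 points, difference 10 to 20 points: 0.05 × 0.10 = 0.005 to 0.05 × 0.20 = 0.010
- Excess share 20 points, same differences: 0.20 × 0.10 = 0.02 to 0.20 × 0.20 = 0.04

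**6. Effect on the specificity interval.** This is the exact binomial probability that a 95% Wilson interval with n = 153 contains a true 90%. The Wilson method is assumed, because the plan names none.

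| Upward shift in enrolled specificity | Coverage of true 90% |
|---|---|
| 0 | 94.3% |
| 0.5 points | 94.1% |
| 1 point | 92.9% |
| 2 points | 86.8% |
| 4 points | 57.3% |

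Every shift shown is inside the plan's 7-point margin. For sensitivity, 2 to 4 points is small beside a half-width of about 14.

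**7. Effect on predictive values.** NPV = (1−p)·Sp / [(1−p)·Sp + p·(1−Se)], where p is the share with hydronephrosis.

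- p = 0.10, Se = Sp = 0.90: 98.8%; with both at 0.92: 99.0%; with both at 0.94: 99.3%
- Se = Sp = 0.90 with p = 0.05 or 0.20 (assumed): 99.4% or 97.3%

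NPV, the measure closest to the rule-out aim in Section 2.2, therefore moves by at most about 1.5 points. PPV = p·Se / [p·Se + (1−p)(1−Sp)] is 32%, 50% or 69% at p = 0.05, 0.10 or 0.20. PPV depends on prevalence in any sample, so that spread is not in itself a sign of bias.

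**The case against.** The strongest reply is that nothing is really in conflict: Sections 2.4.1 and 3.3 say who may be invited, and Section 2.4.2 says when staff get to them. The sentence about convenience also disclaims demographic targeting, so availability is a natural reading. This stands as a possibility; what remains is that Section 2.4.2 does not say it.

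A reader might infer that recruiters will favour easy scans, or will choose patients knowing the radiology result. The documents do not support either inference. No section suggests that ease is judged before approach, and Section 2.3.2 already excludes BMI above 40 and rash over the scanning area by open rule, which narrows the room for undeclared selection. The known-result route needs several things together: an approach after the scan, an available result, a recruiter who is not the scanner, and a recruiter who looked and acted on it. Recruitment normally starts at the order, and how often it starts later is not stated.

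It is also fair that the 57% coverage figure is the far end of an assumed range, and that shifts below 2 points barely matter. Finally, the proposed log would hold counts and reasons, not scan difficulty or results for patients not enrolled, so it cannot directly show the bias. These objections lower the priority. They do not supply the missing approach rule or the missing denominator.

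**Conclusion.** The point holds in a limited form. The plan gives no clear rule for whom to approach, does not keep the radiology result from whoever decides, and records nothing before consent. The documents do not show that selection bias will occur, and they do not establish an outright contradiction.

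The effect runs from negligible, if convenience means availability, to a material loss of interval coverage for specificity under the larger assumed shifts. For sensitivity and NPV the effect is modest throughout the illustration. The figures rest on the assumed easy-scan share and accuracy difference, an assumed 90% sensitivity, the assumed alternative prevalences, the Wilson interval, and the reading of the 90% prevalence as absence of hydronephrosis. This is a cheap improvement of lower priority, and it implies no change to the sample size.

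**What to change.** In Section 2.4.2, replace the convenience clause with:

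> During pre-set periods of team availability, every eligible order is approached consecutively, by a team member who has not opened the radiology report. A log without name or MRN records the order date and a reason code for each eligible patient not approached or declining, including those lost because the report had been opened. The numbers eligible, approached and enrolled will be reported.

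Align Sections 2.4.1 and 3.3 so that the invitation covers all eligible patients whose order falls in these periods. The de-identified log is meant to fit the minimum-necessary principle in Section 2.5.4, and the EPIC order feed already supplies the candidates.

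**Cost.** A short amendment to three sections and a brief log entry for each eligible patient not enrolled; the staff time cannot be worked out from the documents. No new procedure, reader or additional patients are needed.

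**Downsides.** Pre-set periods are still non-random time sampling. Consecutive approach across the emergency department, the floors on two campuses and the ICU takes organization. A few patients will be lost because the report had been opened, mainly those already scanned under the third inclusion criterion; that loss could itself be selective, which is why it is counted.

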2.4.3 Pre-Study Period

2.4.4 Study Period

CONFIDENTIAL: This document is the intellectual property of [name]. Acceptance of this document constitutes the agreement by the recipient that no unpublished information contained herein will be published or disclosed without prior written approval.

5/1/2019 to 10/31/2020

Methods:

2.4.6 Observations and Measurements

1. Presence or absence of hydronephrosis in the right kidney
2. Presence or absence of hydronephrosis in the left kidney
3. If hydronephrosis present: severity of hydronephrosis (mild, moderate, severe)
4. Time taken to obtain ultrasound images of both kidneys
5. Technical difficulty of study as rated by operator (easy, relatively easy, challenging, very challenging)

2.4.6.3 Primary Outcome Measures

1. Sensitivity, specificity, positive and negative predictive value of HCU compared to radiology read (blinded when obtaining data)

2.4.6.4 Secondary Outcome Measures

1. Duration of obtained measurement(s)
2. Interobserver reliability
3. Potential cost reduction

2.4.6.5 Statistical Methods

2.4.6.6 Sample Size

Assuming an alpha error of 0.05, marginal estimation error (d2) of 0.07, and prevalence of 90%, we determined that **170 patients** were to be included to detect a specificity of absence of hydronephrosis to be 90%.

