Renal ultrasonography is most commonly ordered for patients with acute kidney injury, with a main focus on identifying obstruction of the collecting system, a rare but potentially reversible cause of acute kidney injury. While data is lacking regarding the use of POCUS to identify hydronephrosis in an inpatient setting, data from emergency-use of POCUS demonstrates the validity of using POCUS to evaluate for hydronephrosis. In a prospective observational study of emergency department (ED) patients with suspected renal colic compared computed tomography (CT) results with POCUS and found that hydronephrosis on POCUS was predictive of a ureteral stone 88% of the time. These findings suggested that POCUS can be used to first detect hydronephrosis and aid physicians in identifying patients with renal colic¹. Another prospective observational study of emergency physicians without prior training on renal ultrasonography who underwent a short training program and then evaluated patients with presumed renal colic, acute pyelonephritis or documented renal failure with POCUS. Results of POCUS were compared with radiologist-read ultrasound and found that hydronephrosis was detected in 100% of cases and accurately ruled out in 71% of cases².

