2.5.2 Premature Discontinuation

If a subject withdraws from the study, the subject will be replaced in order to provide the required number of evaluable subjects. Subjects will be withdrawn if the investigator decides that discontinuation is in the best interest of the subject, or the subject requests withdrawal from the study.

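### The stated sample-size inputs do not give 170 patients: they give 79 if the 90% means absence of hydronephrosis, or 706 as literally worded

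*Combined protocol and SAP*

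**What the plan says.** The sample-size paragraph (section 2.4.6.6) lists its assumptions as "Assuming an alpha error of 0.05, marginal estimation error (d2) of 0.07, and prevalence of 90" percent. It concludes that 170 patients are needed "to detect a specificity of absence of hydronephrosis to be 90" percent. The Synopsis repeats 170. Neither place gives a formula, a power, a null value, the sidedness of alpha or an allowance for losses.

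Three other places bear on how to read this:

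- Section 2.1 (Background and Significance) describes "obstruction of the collecting system, a rare but potentially reversible cause of acute kidney injury".
- Section 2.4.6.3 names as primary outcomes "Sensitivity, specificity, positive and negative predictive value of HCU compared to radiology read". Sensitivity therefore has the same standing as specificity.
- Section 2.5.2 says of a subject who withdraws that "the subject will be replaced in order to provide the required number of evaluable subjects". Losses are handled by replacement, not by a larger target.

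**The concern.** A margin of error, an anticipated specificity, a prevalence and an alpha, with no power or null value, are the inputs of the standard precision formula for specificity. Put into that formula, they do not return 170.

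The label on the 90% is a second difficulty. In a diagnostic-accuracy calculation, prevalence ordinarily means prevalence of the target condition. A 90% prevalence of hydronephrosis does not fit a Background that calls obstruction rare in this population. The 90% more probably means the share of patients without hydronephrosis, but the text does not say so, and the two readings differ ninefold in the required total.

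Two things are at stake. First, 170 is the plan's only enrolment target, and a reader cannot recover its basis or tell which figure is wrong. Second, the paragraph covers specificity alone. The objective in section 2.2 is to rule out hydronephrosis, so missed cases matter. Once the 90% is defined as absence, it becomes plain how few patients will inform sensitivity.

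**Working it through.** **Inputs.** From section 2.4.6.6: alpha 0.05, margin d = 0.07 (labelled d2), a prevalence of 90%, and specificity Sp = 0.90. Sidedness is not stated; I assume two-sided, z = 1.96. The unit is taken as the patient, because the target is counted in patients.

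**Formula.** Number without hydronephrosis: n₀ = z² × Sp × (1 − Sp) / d². Total: N = n₀ / (fraction without hydronephrosis).

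**Attempt to reproduce 170.**

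n₀ = 1.96² × 0.90 × 0.10 / 0.07² = 0.3457 / 0.0049 = 70.6, so 71.

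| Reading of the 90% | Fraction without hydronephrosis | Total |
|---|---|---|
| Share free of hydronephrosis | 0.90 | 70.6 / 0.90 = 78.4, so 79 |
| Prevalence of hydronephrosis (literal) | 0.10 | 70.6 / 0.10 = 705.6, so 706 |

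Solving backwards, 170 would need 70.6 / 170 = 41.5% of patients free of hydronephrosis, that is 58.5% affected. That matches neither the 90% nor a rare condition.

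**Variants that keep the stated inputs.** The three figures are the totals with no prevalence adjustment, with 0.90 and with 0.10.

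| Variant | Totals |
|---|---|
| One-sided alpha | 50 / 56 / 497 |
| d2 read as d² = 0.07 | 5 / 6 / 50 |
| 0.07 as the full interval width | 283 / 314 / 2823 |
| Continuity correction | 85 / 94 / 843 |

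Requiring the Wilson lower limit to lie within 0.07 of 0.90 gives 111, or 124 after dividing by 0.90. The exact lower limit gives about 120, or about 134. None of these is within 3% of 170.

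**Near-matches, each needing a changed or added input.**

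- d = 0.05 in place of 0.07: 0.3457 / 0.0025 / 0.90 = 153.7, so 154. Adding 10% gives 154 × 1.1 = 169.4. The plan states 0.07 and no inflation.
- One-sided test of 83% against 90% at 80% power: 154.6 / 0.90 = 171.8, so 172. Power and sidedness are not stated.
- Two-sided test of a null of 90% against 83% at 80% power: 166.8, so 167, but only without dividing by 0.90 (186 with it).

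**What 170 delivers if 90% are free of hydronephrosis.**

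- Specificity: 170 × 0.90 = 153 patients. Half-width 1.96 × √(0.09 / 153) = 0.048, or 4.8 points.
- Sensitivity: 170 × 0.10 = 17 patients expected, with a 95% binomial range of 10 to 25. The plan gives no anticipated sensitivity, so the half-widths below are for assumed values. They are Wald figures and approximate at n = 17.

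| Assumed sensitivity | Half-width with n = 17 |
|---|---|
| 80% | 1.96 × √(0.16 / 17) = 0.190 |
| 90% | 1.96 × √(0.09 / 17) = 0.143 |
| 95% | 1.96 × √(0.0475 / 17) = 0.104 |

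Methods suited to small samples give the same picture. If 15 of 17 are detected, the Wilson interval runs from 65.7% to 96.7%. If all 17 are detected, the exact lower 95% limit is 0.025^(1/17) = 0.805, or 80.5%.

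**The case against.** The strongest reply is that 79 is not what the inputs give until a reader has chosen a meaning for the 90%. The phrase about specificity of absence can even be turned round. If absence is the target condition and 90% have it, the formula divides by 0.10 and returns 706. The Background calls obstruction rare as a cause of kidney injury, but gives no prevalence of hydronephrosis among inpatients sent for ultrasound. This stands as a limit: 79 is conditional, and so is the view that the 90% is mislabelled. It does not rescue 170, which neither reading produces.

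Second, the paragraph mixes estimation wording with test wording. A null of 83% can be built as 90% minus the stated margin, and a one-sided test at 80% power then comes within about 1% of 170. Incomplete reporting is therefore a live explanation. Even so, the power and sidedness would have to be supplied from outside the plan, and the result is 172.

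Third, d2 may be d² with a lost superscript. The label should carry little weight, and the conclusion does not rest on it.

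Fourth, 170 exceeds 79, so specificity is not harmed on the preferred reading. That is correct. What remains is a justification that cannot be reproduced and an unstated limit on sensitivity.

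Finally, section 2.4.6 records each kidney separately, and the plan does not say whether accuracy is per patient or per kidney. The precision figures here are per patient. Counting two kidneys per patient as independent would roughly halve the totals, to about 40 or 353, and still would not give 170.

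**Conclusion.** The concern holds. The inputs in section 2.4.6.6 give 79 patients if 90% are free of hydronephrosis, or 706 if 90% have it. They do not give 170 under any standard precision formula tried. The documents do not show whether 170, the 0.07 or a missing input is at fault.

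This is a defect of justification, not a shortfall for specificity. On the absence reading, 170 patients give about ±4.8 points for specificity, tighter than the stated ±7. The practical consequence is for sensitivity: about 17 patients and a half-width of about ±14 points if sensitivity is 90%, which the plan does not disclose.

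These precision figures assume the absence reading, a two-sided 95% interval, analysis per patient, and the assumed sensitivity. The failure to reproduce 170 does not depend on the choice between the two readings. It should be corrected.

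**What to change.** State the formula, say what d2 and the 90% denote, and reconcile them with 170.

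If the basis is precision and the 90% is confirmed as absence of hydronephrosis, keep 170 and replace the prevalence and margin statements with:

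> Assuming absence of hydronephrosis in 90% of patients, 170 patients provide about 153 without hydronephrosis. If specificity is 90%, the two-sided 95% CI half-width is about 4.8 percentage points. About 17 patients with hydronephrosis are expected, so if sensitivity is 90% its half-width is about 14 percentage points.

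If 170 came from a hypothesis test or an inflation, state the null value, power, sidedness or inflation that was used, and keep the sentence on sensitivity.

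The cost is one paragraph of protocol text, with no change in enrolment on either route. Only if the sponsor truly meant a 90% prevalence of hydronephrosis, with the ±7 margin, would the target itself need to be revisited.

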1. SYNOPSIS

Study Title	Hand-carried ultrasound for hydronephrosis	
Objective	Determine if internal medicine trainees can rapidly and accurately rule out hydronephrosis using hand-carried ultrasound	
Study Period	Planned enrollment duration: 18 months Planned study duration: 18 months	
Number of Patients	170	
Study Treatment	none	
Study Design	Prospective Observational	
Inclusion and Exclusion Criteria	
List Inclusion and Exclusion Criteria for your study:
 
Inclusion Criteria:
 
 1. Age >18 years 2. Acute kidney injury or acute kidney disease 3. Retroperitoneal ultrasound ordered or performed within the last 4 hours 
Exclusion Criteria:
 
 1. End-stage renal disease 2. History of kidney transplantation 3. Pregnant women 4. Prisoners 5. Patient unable to provide informed consent 6. Morbid obesity (BMI >40) 7. Current diagnosis of renal cell carcinoma 8. Rash overlying scanning area (left or right flank) 	
Measurements	(1) Presence or absence of hydronephrosis on hand-carried renal ultrasound (2) Severity of hydronephrosis (only when present) on HCU	
Statistical Methodology	Interobserver reliability/ kappa; Sensitivity, specificity, PPV and NPV of HCU performed by trainees compared to read by staff radiologist	

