2.1.1 Preliminary Data

None available

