2.2 Objective

CONFIDENTIAL: This document is the intellectual property of [name]. Acceptance of this document constitutes the agreement by the recipient that no unpublished information contained herein will be published or disclosed without prior written approval.

Evaluate the accuracy of HCU in ruling out hydronephrosis in patients with a diagnosis of acute kidney injury (AKI) or acute kidney disease (AKD) in an inpatient setting. We anticipate potential cost savings for patients and for the healthcare system.

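### Section 2.4.6.6: the stated inputs do not give 170 patients, and if the 90% means hydronephrosis absent, sensitivity rests on about 17 cases

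*Combined protocol and SAP*

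**What the plan says.** Section 2.4.6.6 is the only sample-size text. It begins "Assuming an alpha error of 0.05, marginal estimation error (d2) of 0.07, and prevalence of 90" per cent, and concludes that 170 patients "were to be included to detect a specificity of absence of hydronephrosis to be 90" per cent. It gives no formula, no expected sensitivity and no expected number of hydronephrosis cases, and it does not say what the prevalence is a prevalence of.

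The aim is rule-out. The Synopsis has "Determine if internal medicine trainees can rapidly and accurately rule out hydronephrosis using hand-carried ultrasound", and section 2.2 begins "Evaluate the accuracy of HCU in ruling out hydronephrosis in patients with a diagnosis of acute kidney injury (AKI". Section 2.4.6.3 makes four measures primary without ranking them: "Sensitivity, specificity, positive and negative predictive value of HCU compared to radiology read". It names no confidence interval and no success criterion.

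The documents give little to settle the prevalence. Section 2.1 calls obstruction "a rare but potentially reversible cause of acute kidney injury" but gives no figure. Section 2.1.1, on preliminary data, reads "None available". Patients enter on the criterion "Retroperitoneal ultrasound ordered or performed within the last 4 hours" (section 2.3.1). Section 2.4.6 records each kidney separately, while section 2.4.6.6 counts patients. Section 2.5.2 replaces subjects who withdraw, so no dropout inflation is hidden in the 170.

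**The concern.** There are two linked problems. First, a reader cannot get from the inputs to 170, so the number has no stated justification. Second, the wording leaves open which group of patients carries the precision. In an accuracy study, sensitivity is estimated only from patients with the condition and specificity only from those without it. If one group is a tenth of the sample, the two measures differ about threefold in precision.

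A rule-out claim fails when cases are missed, so it depends mainly on sensitivity. If hydronephrosis is the uncommon state, sensitivity is the less precise measure, and the plan does not tell the reader so. The risk is that a high negative predictive value, which low prevalence produces almost automatically, is presented as a successful rule-out when the data still allow a substantial share of cases to be missed.

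**Working it through.** **Inputs.** From section 2.4.6.6: alpha 0.05, margin d = 0.07, expected value p = 0.90, prevalence 0.90, N = 170. Sidedness is not stated; a two-sided 95% interval is assumed (z = 1.96). Expected sensitivity is not stated, so it is varied. Counts are per patient.

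**1. Trying to reproduce 170.** Number in the relevant group: n = z² p(1−p)/d² = 3.8416 × 0.09/0.0049 = 70.6, so 71. Total N = n divided by that group's share of patients.

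| Reading of 0.07 | n in group | N if share is 0.9 | N if share is 0.1 |
|---|---|---|---|
| half-width (d = 0.07) | 71 | 79 | 706 |
| total width (d = 0.035) | 283 | 314 | 2,823 |
| d squared (d² = 0.07) | 5 | 6 | 50 |

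A one-sided version with d = 0.07 gives 50, 56 and 497. None of these is 170.

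**2. What 170 delivers if the 90% means absent.** Expected cases: 170 × 0.10 = 17, with a 95% sampling range of 10 to 25. Non-cases: 153.
- Specificity at 90%: 1.96 × √(0.09/153) = 0.048, or 4.8 points.
- Sensitivity at 90%: 1.96 × √(0.09/17) = 0.143, or 14.3 points.

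**3. Sensitivity over a range of assumptions.** Half-width in points = 100 × 1.96 × √(Se(1−Se)/cases):

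| Assumed hydronephrosis prevalence (cases) | Se 80% | Se 85% | Se 90% | Se 95% |
|---|---|---|---|---|
| 5% (8.5) | 26.9 | 24.0 | 20.2 | 14.7 |
| 10% (17) | 19.0 | 17.0 | 14.3 | 10.4 |
| 20% (34) | 13.4 | 12.0 | 10.1 | 7.3 |

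The normal approximation is rough with so few cases. At 90% sensitivity the mean exact (Clopper-Pearson) half-width is about 24, 16 and 11 points at the three prevalences.

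**4. Exact 95% lower bounds.** 17/17: 80.5%; 16/17: 71.3%; 15/17: 63.6%. Perfect detection of other case counts gives 63.1% for 8/8 and 89.7% for 34/34.

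**5. Which measure the plan has sized.** With the 90% as absent:
- If the named measure is ordinary specificity, 170 gives 4.8 points, better than 7, and the plan sets no precision for sensitivity.
- If absence is treated as the target condition, the named measure is sensitivity for hydronephrosis, and 17 cases do not deliver 7 points.

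With the 90% as present, there are 153 cases and 17 non-cases. Sensitivity has 4.8 points and specificity 14.3, so a 7-point target for ordinary specificity is the one missed.

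**6. Why negative predictive value does not replace sensitivity.** NPV = Sp(1−p)/[Sp(1−p) + (1−Se)p], where p is now hydronephrosis prevalence. With p = 0.10, Sp = 0.90 and Se = 0.50, NPV = 0.81/(0.81 + 0.05) = 94.2%. Calling every patient negative gives 90%.

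**The case against.** **The margin belongs to another measure.** A reader might infer that the plan promised 7 points for sensitivity and delivers 14. The documents do not support this. The 0.07 is attached to a specificity phrase, and the contrast holds only if absence is the target condition and 0.07 is a half-width. The label d2 leaves even that open: if 0.07 is d squared, d is √0.07 = 0.265, wider than 14 points. This objection stands.

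**Rule-out may mean specificity here.** Section 2.1 summarises an emergency-physician study by setting detection in all cases against correct rule-out in 71%. The second figure most naturally means correct negatives among patients without hydronephrosis. On that usage the objective and the sample size may agree. This may explain why specificity was sized, but it does not produce 170. Nor does it alter what a negative scan must show, namely that few cases are missed. Sensitivity is a primary measure in any event.

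**The 90% is not known to mean absent.** In section 2.1, rare describes obstruction as a cause of acute kidney injury, not hydronephrosis among patients with an ultrasound ordered. This stands, and the 17 cases are conditional on it.

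**A power calculation may lie behind 170.** One-sample tests of 0.83 against 0.90 with 80% power come close (167 or 172, depending on direction, sidedness and prevalence adjustment). Section 2.4.6.6 states no power and no null value, so the match may be coincidence.

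**NPV has equal standing, and 50% sensitivity is a deliberately poor test.** At 90% sensitivity, 90% specificity and 10% prevalence, NPV is 98.8%. That is fair, but a weak test also exceeds 90%, so NPV alone does not separate the two well.

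**Counting kidneys would help.** At most 34 affected kidneys would arise from 17 cases, if all were bilateral. That gives 10.1 points at 90% sensitivity before allowing for within-patient correlation.

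**The study estimates accuracy and tests no hypothesis.** Requiring a minimum sensitivity would change its aim. This stands, so a minimum is optional.

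**Conclusion.** The sample-size statement is wrong as written and should be fixed. That 170 does not follow from the stated inputs holds whichever way the 90% and the 0.07 are read, under the standard precision formula. The undefined prevalence and target condition also need no inference.

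The consequence for sensitivity is conditional. If hydronephrosis is absent in 90% of patients, sensitivity rests on about 17 cases, with a half-width of about 10 to 19 points over assumed sensitivities of 95% down to 80%, against 4.8 points for specificity at 90%. After perfect detection of 17 cases, the exact interval still allows about 20% to be missed. If the 90% means present, the sensitivity concern falls away and specificity has the wide interval.

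A reader might also infer that the trial must enrol about 706 patients. The documents do not support that: 706 follows only if the 7-point half-width was meant for the group that makes up 10% of patients. The defect is in what the plan states about its precision; it does not show that 170 is the wrong number to enrol.

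**What to change.** Keep N = 170.

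**Section 2.4.6.6**
- Define the target condition, what the 90% refers to, and the unit of analysis (patient or kidney).
- Replace the calculation with the formula and the margin that 170 delivers for the named measure.
- State the expected number of hydronephrosis cases and the exact-interval precision of sensitivity over a range of prevalence (for example 5% to 20%) and of sensitivity (80% to 95%).

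**Section 2.4.6.3**
- Report sensitivity with an exact 95% confidence interval, or one that allows for two kidneys per patient if the kidney is the unit.
- Base the rule-out conclusion on that interval and not on NPV alone, and say that it may be inconclusive.
- Show NPV beside 1 minus the observed prevalence.

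A minimum sensitivity fixed before analysis is optional. If one is set and the lower bound must exceed it, note that with 17 cases no minimum above about 80% can be met, even with perfect detection.

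**Cost.** Protocol and analysis wording only, with no new patients or data. No precision is gained, the stated precision becomes less favourable, and the rule-out result may be inconclusive.
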